7.4.3 Cancer History

Cancer history data, previous systemic cancer therapy, previous radiation therapy may be summarized for the treated population.

Subject listings of cancer history, previous systemic cancer therapy, previous radiation therapy will also be provided.

7.4.4 Surgical Procedures

Subject listings of any on-study surgical procedures and any blood transfusions will be provided.

7.4.5 Previous and Concomitant Medications

All prior and concomitant medications will be coded using WHODrug Global, B3 March 2018 or later.

Prior medications are defined as those medications that started and ended prior to Day 1, the first exposure to study drug (RMC-4630 and sotorasib combined). Concomitant medications are all medications taken during the study period, including those started before but ongoing at first dose. If a medication start or end date is fully missing, and it is unclear as to whether the medication is

prior or concomitant, it will be assumed that it is concomitant. If a medication start date or end date is partially missing, then the date will be imputed based on rules described in Section 5.2

Summary of concomitant medication will be presented by WHO Anatomical Therapeutic Chemical (ATC) and preferred term (PT) by the initial combination dose level and overall using treated population. A subject will only be counted once per ATC and once per PT within a dose level.

Listings for prior and concomitant data and protocol specified prohibited medications will be provided.

7.5 Study Drug Exposure and Compliance

Duration of exposure and relative dose intensity will be calculated and summarized with descriptive statistics using treated population.

Number and percent of subjects experienced dose change (dose missed, reduced, and discontinued), and primary reason for dose change will also be summarized by dose level and overall.

Listing of drug exposure from dose administration log including derived cumulative planned dose, cumulative actual dose, and relative dose intensity for each subject will be provided. Listing of drug dispenses including lot/kit number, and list of change in dose assignment/frequency for each treatment will also be provided.

7.6 Efficacy Analyses

The efficacy endpoints of ORR, DCR, and DOR will be based on the treated population, and will be summarized by the initial combination dose level. As supportive analyses, these efficacy endpoints will also be summarized for the efficacy-evaluable population. PFS and OS will be summarized on the all-treated population. Efficacy analyses will also be presented by Cohort 1 and Cohort 2 at the expansion dose level.

Handling of Missing Efficacy Data

- For analyses of binary endpoints, subjects among the analysis population who have not achieved the outcome of interest by the time of analysis will be considered a non-responder for the analysis.
- For time to event endpoints, subjects without post-baseline assessments will be censored at the date of the first dose of study drug.

7.6.1 Primary Efficacy Analysis

Objective Response Rate (ORR)

The primary endpoint ORR is defined as the proportion of subjects who have achieved either Complete Response (CR) or Partial Response (PR) per RECIST1.1. A CR or PR should be confirmed by a repeat assessment no less than 28 days.

ORR and the corresponding 95% two-sided exact binomial confidence interval using the Clopper-Pearson method will be presented.

Frequency and percentages for individual best overall response (BOR) which includes CR, PR, Stable Disease (SD), Progressive Disease (PD), and Not Evaluable (NE) per RECIST v1.1 (see Appendix B) will also be summarized.

In addition, summary of best percent change from baseline in tumor size by best overall response using efficacy evaluable population will be presented. A waterfall and spaghetti plots of percent change from baseline for sum of diameters (SOD) by best overall response will also be presented.

7.6.2 Secondary Efficacy Analysis

Disease Control Rate (DCR)

DCR is defined as the proportion of subjects who achieve a CR or PR or SD per RECIST v1.1. A CR or PR should be confirmed by a repeat assessment no less than 28 days, and SD requiring the minimum duration of 5 weeks from initiation of first dose of study drug ((i.e., at least 35 days between treatment start and scan date qualifying the subject for a BOR of SD)).

DCR and the corresponding 95% two-sided exact binomial confidence interval using the Clopper-Pearson method will be presented.

Duration of Response (DOR)

DOR is defined as the interval from the first documentation of CR or PR to first documentation of definitive disease progression or death due to any cause, whichever occurs first.

Subjects who are still alive and free from progression at the time of data cutoff date, or lost to follow-up, or discontinued from the study or initiated subsequent anticancer therapy will be censored at the last adequate tumor assessment. Subjects who never achieve a response (PR or better) will be excluded from the analysis of DOR. (Refer to censoring rule document)

$$DOR = (date\ of\ event/censor - first\ date\ of\ confirmed\ CR\ or\ PR + 1) / 30.4375.$$

The Kaplan-Meier method will be used to estimate DOR curves and corresponding quartiles. The Kaplan-Meier median will be calculated with a two-sided 95% confidence intervals. If the number of responders is less than 5, DOR data will be provided in a subject listing.

A Swimmer plot of response and duration of treatment will be presented.

Progression Free Survival (PFS)

PFS is defined as the interval from the first dose of study treatment to documented disease progression per RECIST v1.1 or death due to any cause, whichever occurs first.

For subjects who are still alive and free from progression at the time of data cutoff date, or lost to follow-up, or discontinued from the study, or initiated subsequent anticancer therapy, PFS will be censored at the last adequate tumor assessment.

For subjects with PD or death after two or more missing consecutive scheduled assessments, or if a subject initiated subsequent anticancer therapy before the PD date or death prior to first post-baseline scan, PFS will be censored at the last tumor assessment visit prior to the occurrence of the consecutive missing visits or prior subsequent anticancer therapy respectively.

Subjects who do not have post-baseline evaluable tumor assessment, PFS will be censored at day 1.

$$PFS = (date\ of\ event/censor - date\ of\ first\ dose\ of\ study\ drug + 1) / 30.4375.$$

PFS will be summarized for the all-treated population. The Kaplan-Meier method will be used to estimate PFS curves and corresponding quartiles. The Kaplan-Meier median will be calculated with a 2-sided 95% confidence intervals.

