9.4.1. Efficacy Analyses

The statistical analysis plan will be developed and finalized before database lock. Below is a summary of the planned statistical analyses.

Unless otherwise specified, efficacy analyses will be based on the efficacy-evaluable population and will be summarized by the initial combination dose level. Efficacy analyses will be presented for Cohort 1 and Cohort 2 separately, and for the overall study population.

The primary efficacy endpoint is ORR, defined as the proportion of subjects who achieve a CR or PR per RECIST v1.1. The estimated proportion and the corresponding 95% two-sided exact CI using the Clopper-Pearson method will be derived for ORR.

Secondary efficacy endpoints and analyses include the following:

- DCR is defined as the proportion of subjects who achieve a CR or PR or SD per RECIST v1.1. DCR will be analyzed similarly as ORR.
- DOR is defined as the interval from the first documentation of CR or PR to first documentation of definitive disease progression or death due to any cause, whichever occurs first. Subjects who are still alive and free from progression at the time of the data cutoff date, are lost to follow-up, have discontinued from the study, or have initiated subsequent anticancer therapy will be censored at the last adequate tumor assessment. Subjects who never achieve a response (PR or better) will be excluded from the analysis of DOR.
- PFS is defined as the interval from the first dose of study treatment to documented disease progression per RECIST v1.1 or death due to any cause, whichever occurs first. Subjects who are still alive and free from progression at the time of the data cutoff date, are lost to follow-up, have discontinued from the study, or who have initiated subsequent anticancer therapy will be censored at the last adequate tumor assessment. PFS will be summarized for the all-treated population.

- Overall survival (OS) is defined as the interval from the first dose of study treatment to death due to any cause. Subjects who are not known to have died will be censored at the last known alive date. OS will be summarized on the all-treated population.

The Kaplan-Meier method will be used to estimate DOR, PFS and OS curves and corresponding quartiles. The Kaplan-Meier median will be calculated with a two-sided 95% CI.

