- Quantification of biomarker expression (protein, RNA, and DNA levels) as appropriate in ctDNA and archival tumor tissues (or fresh, if archival tumor is not available)

4. Pharmacokinetic (PK)

See [7.8](#) of this SAP.

5. Analysis Populations

Treated Population

Includes all subjects who have taken at least one dose of study treatment.

Efficacy-Evaluable Population

Includes all subjects with measurable disease at baseline, who have taken at least one dose of study treatment and (1) underwent one post-baseline response assessment or (2) who died or (3) had clinical progression prior to the first post-baseline response assessment.

DLT-Evaluable Population

Includes all subjects enrolled during safety lead-in in the treated population who have received at least 80% of planned dose of sotorasib and at least 4 of 6 doses of RMC-4630 in Cycle 1 and have been observed for safety assessments for the full 21 days of the DLT evaluation period. Subjects who experience a DLT within the DLT period will be considered DLT evaluable regardless of the amount of study treatment received or completion of the observation period.

6. Data Handling

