7.6.3 Subgroup Analysis

Efficacy analyses of ORR (confirmed and unconfirmed), DCR, PFS, and OS by demographics and baseline characteristics subgroups will be performed for all treated and efficacy evaluable populations.

Other efficacy analyses may also be performed in subgroups, as applicable, using the same analysis methods as described for the overall population.

Overall Survival (OS)

OS is defined as the interval from the first dose of study drug to death, from any cause. Subjects who are not known to have died will be censored at the last known alive date. (Refer to censoring rule document).

$$OS = (date\ of\ event/censor - date\ of\ first\ dose\ of\ study\ drug + 1) / 30.4375.$$

OS will be summarized on the all-treated population. The Kaplan-Meier method will be used for analyses of OS. The Kaplan-Meier median with 95% two-sided confidence intervals will be estimated.

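### The SAP's Day 1 censoring rule for PFS has no exception for subjects who die before a post-baseline scan, which contradicts its own event definition

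*SAP*

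**What the plan says.** SAP 7.6.2 defines PFS as the time from first dose "to documented disease progression per RECIST v1.1 or death due to any cause, whichever occurs first". Protocol 9.4.1 has the same definition: "the first dose of study treatment to documented disease progression per RECIST v1.1 or death due to any cause, whichever occurs first". Neither requires a scan for a death to count.

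Two SAP sentences then deal with subjects who have no follow-up assessment:

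- SAP 7.6.2: "Subjects who do not have post-baseline evaluable tumor assessment, PFS will be censored at day 1".
- SAP 7.6, under the handling of missing efficacy data: "For time to event endpoints, subjects without post-baseline assessments will be censored at the date of the first dose of study drug".

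One further sentence in SAP 7.6.2 mentions early death. Its first part deals with events that follow at least two missed scans in a row. Its second part reads: "if a subject initiated subsequent anticancer therapy before the PD date or death prior to first post-baseline scan, PFS will be censored at". It then names two censoring dates in turn: the scan preceding the missed visits, and the scan preceding the new therapy.

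OS has its own rule, printed under SAP 7.6.3: "Subjects who are not known to have died will be censored at the last known alive date". PFS and OS are both summarised in all treated subjects. Protocol 9.4.1 has no Day 1 rule; it censors PFS at the last adequate tumor assessment.

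**The concern.** The event definition and the censoring rule give the same subject two different outcomes. The plan foresees such subjects: the efficacy-evaluable population in SAP section 5 includes those "2) who died or (3) had clinical progression prior to the first post-baseline response assessment". Because PFS uses all treated subjects, they are in the analysis set.

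Applied literally, the Day 1 rule removes these deaths from the event count and from the risk set, which can only raise the Kaplan-Meier curve. PFS is reported by dose level and cohort, so one or two such subjects in a small group can move the median.

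There is also a documentation point. SAP section 1 says the SAP supersedes the protocol's statistical text and that substantial differences will be identified. Section 10 identifies none. If censoring of early deaths is intended, it is an undeclared change; if it is not intended, the sentence is wrong. Day 1 censoring of *living* subjects without a scan is a reasonable elaboration of the protocol and is not at issue.

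**Working it through.** **One subject under both rules.** Protocol 8.1 puts the first scheduled scan at the start of Cycle 3; with 21-day cycles that is about Day 43. Take a subject who dies on Day 30 with no scan. The SAP formula is (date − first dose date + 1)/30.4375.

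- By the definition: event at 30/30.4375 = 0.99 months.
- By the Day 1 rule: censored at 1/30.4375 = 0.03 months.

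**Does another sentence settle it?** The sentence on death before the first scan is itself a censoring sentence. It gives two dates, one for missed visits and one for new therapy. That hints that early death is an event unless new therapy came first, but the sentence does not say so. The censoring rule document is cited for DOR and OS, not in the PFS text, and was not available. Nor was the Standard Programming Specification.

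**Reach of the two sentences.** The 7.6.2 sentence speaks of *evaluable* assessments, so it also catches a subject whose only post-baseline scan was not evaluable and who then died. The 7.6 bullet omits that word but covers all time-to-event endpoints, and so formally includes OS, against the OS rule.

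**Size.** Let k of N subjects die before any post-baseline scan, with no other censoring up to time t. The correct estimate is (number event-free at t)/N; the literal rule gives (number event-free at t)/(N − k). So

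S_rep(t) = S(t) × N/(N − k).

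The reported median solves S(t) = 0.5(1 − k/N). For exponential PFS with median m,

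t = m × [1 − log2(1 − k/N)].

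Inputs:

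- m = 6.3 months, assumed (phase 1 sotorasib NSCLC figure, protocol 2.1.2).
- N = 46, the planned total, and N = 20, the low end expected at the expansion dose (SAP 2.3).
- k = 0 to 2, assumed; the documents do not give it.

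True six-month PFS is 0.5^(6/6.3) = 51.7%.

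| N | k | Reported median (months) | Shift (months) | Reported six-month PFS |
|---|---|---|---|---|
| any | 0 | 6.30 | 0 | 51.7% |
| 46 | 1 | 6.50 | +0.20 (3%) | 52.8% |
| 46 | 2 | 6.70 | +0.40 (6%) | 54.0% |
| 20 | 1 | 6.77 | +0.47 (7%) | 54.4% |
| 20 | 2 | 7.26 | +0.96 (15%) | 57.4% |

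A separate Kaplan-Meier illustration put the early deaths at Day 30 and gave all other subjects events after Day 43, with a residual median of 6.3 months. For N = 20 and k = 2 the median was 6.3 months with deaths counted and 7.2 under the literal rule: the same direction and a similar size.

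**Ceiling on k.** Under the same exponential model, the share with *any* PFS event by Cycle 3 Day 1 (42 days = 1.38 months) is 1 − 0.5^(1.38/6.3) = 14.1%, that is 6.5 of 46 or 2.8 of 20. This includes progressions, so it bounds k loosely and does not estimate it. At N = 20, k = 2 is already near the upper end.

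**The case against.** The best reply is that context favours death prevailing. The event is defined first, the opening censoring sentence is mainly about subjects alive and progression-free, and the 7.6 bullet concerns missing data, which an observed death is not. For OS, the specific rule would govern over a general bullet. A sensible programmer would probably code it that way. That is fair, and it is why the finding is confined to the literal reading; but the text does not say it.

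Few subjects are likely to be affected. Eligibility requires a life expectancy of at least 3 months. Imaging may be repeated whenever progression is suspected, and a scan is also due at end of treatment. Only those who die with no evaluable scan of any kind fall under the rule. This stands, and it limits k.

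The shifts are also small against sampling error. With no censoring, an approximate 95% interval for a 6.3-month median, 6.3 × exp(±1.96/√N), is 4.1 to 9.8 months at N = 20 and 4.7 to 8.4 at N = 46. This stands too, but the shift is a bias in one known direction and can be avoided by wording.

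Finally, inserting an exception for deaths in the two sentences might seem enough. That would remove the main conflict, but would leave the ambiguous sentence on early death and new therapy as it is.

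**Conclusion.** The conflict is real as written: followed literally, the Day 1 rule codes a defined PFS event as a censoring and overstates PFS, and no available text resolves it. On the assumptions above, the median is overstated by 0.20 to 0.40 months at N = 46 and 0.47 to 0.96 months at N = 20 for one or two such deaths. The overstatement is zero if there are none or if the programming already counts them as events.

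The consequence is limited. PFS is secondary, no hypothesis is tested and the primary ORR is untouched. Early deaths would still show in OS (under its own rule) and in the all-cause death summary of SAP 7.7.3. It should still be corrected before database lock.

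**What to change.** 1. **Day 1 sentence in SAP 7.6.2.** Replace with: *Subjects with no post-baseline evaluable tumor assessment who have not died are censored at Day 1. A death before the first such assessment is a PFS event on the date of death, unless it follows the start of subsequent anticancer therapy or two or more consecutive missed scheduled assessments. In those cases PFS is censored at the last post-baseline assessment before the therapy or the missed visits, or at Day 1 if there is none.*
2. **Sentence on missed visits and new therapy in SAP 7.6.2.** Reword to match, with the same Day 1 fallback. Without it, a subject whose last assessment before new therapy or missed visits is the screening scan could be censored before first dose. Table 1 of the protocol allows that scan 28 days earlier, giving (−28 + 1)/30.4375 = −0.89 months.
3. **Bullet in SAP 7.6.** Limit it to PFS in subjects without an event, and exclude OS.
4. **Related documents.** Align the censoring rule document and the programming specification. List in SAP section 10 any retained censoring of deaths that differs from the protocol.

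The cost is wording only. Reported PFS is unchanged if there are no such deaths or they are already coded as events; otherwise it becomes slightly less favourable.

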7.6.3 Subgroup Analysis

Efficacy analyses of ORR (confirmed and unconfirmed), DCR, PFS, and OS by demographics and baseline characteristics subgroups will be performed for all treated and efficacy evaluable populations.

Other efficacy analyses may also be performed in subgroups, as applicable, using the same analysis methods as described for the overall population.

Overall Survival (OS)

OS is defined as the interval from the first dose of study drug to death, from any cause. Subjects who are not known to have died will be censored at the last known alive date. (Refer to censoring rule document).

$$OS = (date\ of\ event/censor - date\ of\ first\ dose\ of\ study\ drug + 1) / 30.4375.$$

OS will be summarized on the all-treated population. The Kaplan-Meier method will be used for analyses of OS. The Kaplan-Meier median with 95% two-sided confidence intervals will be estimated.

7.7 Safety Analyses

Safety endpoints of the study are the incidence, nature, and severity of treatment-emergent adverse events (TEAEs), SAEs, clinical laboratory tests, vital signs, and ECGs.

Adverse events (AEs) will be collected from the date that informed consent was signed. Verbatim terms for each AE will be coded using MedDRA Version 25.0 or later and graded per the NCI CTCAE Version 5.0 or later. Treatment-emergent adverse event (TEAE) is defined as those AEs with an onset on or after the date of the first dose of study intervention and within 30 days of last known dose of study intervention. Treatment-related AEs are treatment-emergent AEs reported as related to RMC-4630 or sotorasib.

All AE summaries will be presented for the initial combination dose level and overall using the treated population.

Safety Stopping Rules

During dose expansion after the final expansion dose has been selected, evaluation of all Grade 4 or higher treatment-related adverse event rates will be conducted to assess if the unacceptable toxicity threshold has been reached. If this threshold is met, enrollment to dose expansion will be halted pending review of safety data. After reviewing the totality of data from both CodeBreaK 101C and cumulative data from this study, one of the following actions may be taken:

1. Terminate the study
2. Amend the protocol to potentially improve the benefit/risk for subjects (e.g., increase safety monitoring, modify dose/schedule, mandate premedication)
3. Continue dose expansion without any changes

The stopping rules use a Bayesian approach to pause the enrollment if the posterior probability is $\geq 80\%$ that the Grade 4 or higher treatment-related adverse event rate is greater than 20%. The stopping boundaries shown in Table 1 assume a prior distribution of Beta (0.4, 1.6). The operating characteristics with the pre-specified batch size of 10 new subjects are summarized in Table 2.

Table 1: Stopping Boundary by Number of Subjects

Number of Subjects Treated	Number if Subjects with Grade 4 or Higher Treatment Related Adverse Events to Halt Enrollment
10	≥ 4
20	≥ 6
30	≥ 9
40	Expansion Complete

Table 2: Operating Characteristics of Stopping Rules

True Grade 4 or Higher Treatment-Related Adverse Event Rate	Probability of Early Stopping of Dose Expansion	Average Dose Expansion Sample Size
0.1	2.1%	39
0.15	9.7%	38
0.2	25.8%	34
0.25	47.7%	29
0.3	69.2%	23

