8.3.1. Time Period and Frequency for Collecting AE and SAE Information

Monitoring and recording of AEs and SAEs will be conducted throughout the study. After the signing of the ICF, but prior to initiation of study treatment, only SAEs caused by a protocol-mandated treatment will be collected (eg, SAEs related to invasive procedures, such as biopsies or medication washout). Any medical occurrence that begins before the start of study treatment but after obtaining informed consent, and which is not considered an SAE caused by a protocol-mandated treatment, will be recorded on the Medical History/Current Medical Conditions Section of the eCRF rather than the AE section.

All AEs and SAEs will be collected from the start of treatment until 30 days after the last dose, or upon initiation of alternative cancer treatment, whichever occurs first. After this period, investigators should report only SAEs that are thought to be related to RMC-4630 and/or sotorasib.

Any SAE that is determined to be study-treatment related (possibly, probably, or definitely related) will be followed to resolution or stabilization, until it is determined to be irreversible by the investigator, the subject is lost to follow-up, or it has been determined that the study treatment is not the cause of the AE/SAE, whichever occurs first. After this period, investigators should report only SAEs that are thought to be related to RMC-4630 and/or sotorasib.

All SAEs will be recorded and reported to the Sponsor or designee within 24 hours of investigator awareness, as indicated in [Appendix 3](#). The investigator will submit any updated SAE data to the Sponsor within 24 hours of it being available. During the Extended-Use phase of the study, only SAEs (irrespective of causality) and related AEs will be reported in the EDC. All SAEs will also be reported on the SAE Report Form.

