8.3.3. Follow-Up of AEs and SAEs

After the initial AE/SAE report, the investigator is required to proactively follow each subject at subsequent visits/contacts through the last study visit. All AEs (regardless of relationship to study treatment) and SAEs determined not to be study-treatment related (ie, not related and unlikely related) will be followed through the last study visit and be noted as “continuing” if not resolved at this visit.

All SAEs considered study-treatment related (possibly, probably, or definitely related) will be followed until resolution, stabilization, is determined to be irreversible by the investigator, the subject is lost to follow-up (as defined in [Section 7.3](#)), or it has been determined that the study

treatment is not the cause of the AE/SAE, whichever occurs first. The investigator will submit any updated SAE data to the Sponsor within 24 hours of it being available. During the Extended-Use phase of the study, only SAEs (irrespective of causality) and related AEs will be reported in the EDC. All SAEs will also be reported on the SAE Report Form. Reporting of AEs/SAEs will end after the subject initiates alternative cancer treatment.

Further information on follow-up procedures is given in [Appendix 3](#).

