- Summary of TEAEs leading to dose modification of sotorasib by PT
- Summary of TEAEs leading to dose modification of sotorasib by SOC and PT
- Summary of TEAEs leading to dose modification of RMC-4630 or sotorasib by PT
- Summary of TEAEs leading to death by SOC and PT
- Summary of ECI by category, sub-category, and PT
- Summary of time to onset of ECI by category and sub-category

Treatment-related AEs include those events considered by the investigator to be possibly, probably, or definitely related to study drug (RMC-4630 or sotorasib). AEs with missing relationship status will be classified as related.

If the same PT is reported multiple times for a subject within the same SOC, that PT will only be reported once within that SOC. As with the PT, if a subject has multiple reported events within the same SOC, that SOC will only be reported once. If a subject experiences the same AE with more than one severity, or with more than one relationship to study intervention, the most severe rating or the stronger causal relationship to study drug(s) will be assigned to the event. Any missing severity or outcome will not be imputed and classed as unknown/missing.

Subject listings of all reported AEs, SAEs, AEs leading to dose reduction, treatment interruption, treatment discontinuation from the study, and death will be provided. The listings will be sorted by subject ID, study day, SOC/PT/verbatim term, and severity grade.

Deaths

Summary listing of reported death by any cause will be provided. The number and percentage of subjects experiencing deaths (all-cause) and causes of deaths will be summarized, and will also be categorized as death within or beyond 30 days of last dose of study drugs which occurs later.

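### SAP 7.7 ties treatment-related AEs to the 30-day TEAE window, so late related SAEs that sites must report have no place in the related-event tables and, read literally, none in the stopping count

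*SAP*

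**What the plan says.** **Analysis definition.** SAP 7.7 defines a TEAE by onset from the first dose and "within 30 days of last known dose of study intervention". The next sentence builds the related category on it: "Treatment-related AEs are treatment-emergent AEs reported as related to RMC-4630 or sotorasib".

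**Tables.** SAP 7.7.3 lists the planned summaries. All those for related events, serious or not, are titled as TEAEs or serious TEAEs, and so is the overview table.

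**A second description.** Later in SAP 7.7.3 the same term is described by the investigator's causality categories (possibly, probably or definitely related), with no time limit.

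**Stopping rule.** Also in SAP 7.7, during expansion "evaluation of all Grade 4 or higher treatment-related adverse event rates will be conducted". No other definition of related is given there. Protocol 9.4.2 states the same rule and mentions no window.

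**Collection.** Protocol 8.3.1 has two stages. First, "All AEs and SAEs will be collected from the start of treatment until 30 days after the last dose", or until alternative cancer treatment starts if that is earlier. Then: "After this period, investigators should report only SAEs that are thought to be related to RMC-4630 and/or sotorasib". Footnote 17 to the Schedule of Activities says the same. Protocol 8.3.3 adds: "Reporting of AEs/SAEs will end after the subject initiates alternative cancer treatment". The end of footnote 17 agrees with that sentence.

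**The concern.** The protocol deliberately collects one kind of event after day 30: those that are both serious and attributed to study drug. The SAP's definition then leaves exactly these events without an incidence table. SAP Section 3 names TEAEs and SAEs as separate items of the safety endpoint, yet the SAE tables cover only serious TEAEs.

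The omission works in one direction. It can lower the count of related serious events but never raise it. If the same definition governs the stopping rule, a late related Grade 4 or 5 SAE does not add its subject to the number compared with the boundary.

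**Working it through.** **1. Follow one event through the plan.** Take a Grade 4 SAE judged related, with onset 31 days or more after the last dose and before any alternative cancer treatment.

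| Place | Outcome as written |
|---|---|
| Protocol 8.3.1 | Reported by the site |
| SAP 7.7, TEAE | Not a TEAE (onset outside the window) |
| SAP 7.7, treatment-related AE | Not included (must be a TEAE) |
| SAP 7.7.3, related-AE and related-SAE tables | Excluded by title |
| SAP 7.7.3, subject listings | Included |
| SAP 7.7.3, death summary | Included only if fatal; all-cause, split at 30 days |
| SAP 7.7, stopping count | Excluded if the 7.7 definition applies |

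**2. Reproduce the stopping boundaries (SAP 7.7, Table 1).** Inputs from SAP 7.7: prior Beta(0.4, 1.6); halt if P(rate > 0.20) ≥ 0.80; looks after 10, 20 and 30 treated subjects. With r affected subjects among n, the posterior is Beta(0.4 + r, 1.6 + n − r). The boundary is the smallest r that meets the criterion.

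| n | At the boundary | One subject fewer |
|---|---|---|
| 10 | r = 4, Beta(4.4, 7.6): 0.895 | r = 3, Beta(3.4, 8.6): 0.719 |
| 20 | r = 6, Beta(6.4, 15.6): 0.826 | r = 5, Beta(5.4, 16.6): 0.666 |
| 30 | r = 9, Beta(9.4, 22.6): 0.885 | r = 8, Beta(8.4, 23.6): 0.783 |

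All three boundaries reproduce. At every look, one uncounted subject takes the posterior below 0.80 and turns a halt into a continue. This needs no assumption about how common late events are.

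**3. Reproduce the operating characteristics (SAP 7.7, Table 2).** Exact sequential binomial enumeration with these boundaries and a maximum of 40:

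| True rate | Stopping probability, SAP / recomputed | Average size, SAP / recomputed |
|---|---|---|
| 0.10 | 2.1% / 2.05% | 39 / 39.47 |
| 0.15 | 9.7% / 9.73% | 38 / 37.62 |
| 0.20 | 25.8% / 25.79% | 34 / 33.89 |
| 0.25 | 47.7% / 47.73% | 29 / 28.77 |
| 0.30 | 69.2% / 69.20% | 23 / 23.41 |

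Table 2 is numerically correct for the rate of whatever event is counted.

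**4. Illustration only.** The documents give no frequency of late related events. Assume that a share f of the subjects with a Grade 4 or higher related event have it only after the window. The counted rate is then true rate × (1 − f); for example, 0.25 × 0.90 = 0.225.

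| True rate | f = 0 | f = 5% | f = 10% | f = 20% |
|---|---|---|---|---|
| 0.25 | 47.7% | 42.0% | 36.4% | 25.8% |
| 0.30 | 69.2% | 63.2% | 56.7% | 43.2% |

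For a given f these are the largest possible effects, because they assume that every late event would already be known at the look in question.

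**The case against.** **The stopping-count part is an inference.** Protocol 9.4.2 has no window, and SAP 7.7.3 describes the term by causality alone. SAEs reach the sponsor within 24 hours (Protocol 8.3.1), and the internal safety committee reviews emerging data (Protocol 8.3.6.2). Nothing says that the live count is filtered by the SAP's TEAE definition. This stands as a limit on the claim. Against it, the rule and the narrow definition sit in the same SAP section, and SAP Section 1 says the SAP supersedes the protocol's statistical considerations.

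**The affected group is small.** Treatment must have stopped, more than 30 days must have passed, and the event must be known before a look. Many late events would come after the look under any definition. A subject with an earlier Grade 4 or higher related event is already counted. Follow-up after treatment is telephone contact for survival and anticancer treatment (SAP 2.2.3), and Protocol 8.3.3 ends reporting once alternative cancer treatment starts. All of this stands, and it is why the figures in step 4 are not estimates.

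**The 30-day window has a reason.** It matches the period of full AE collection. Pooling later, selectively reported events with fully collected ones mixes different levels of ascertainment. This supports flagging late events or showing them separately, but not leaving them untabulated.

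**The consequence is limited.** A crossed boundary pauses enrollment for review, and continuing unchanged is a permitted outcome. No hypothesis is tested.

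**Stronger readings.** A reader might infer that the pause rule fires less often than Table 2 states. The documents do not support that: Table 2 is conditional on the counted rate and reproduces. A reader might also infer that these events disappear from the report. They do not: they remain in listings, and fatal ones in the death summary. But a listing gives no incidence.

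**Conclusion.** The concern holds for the tables. As the SAP is written, related SAEs with onset more than 30 days after the last dose are collected but fall outside all related-AE and related-SAE incidence summaries. The causality-only wording in SAP 7.7.3 does not cure this, because the table titles still restrict to TEAEs.

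For the stopping rule it holds on a literal reading of SAP 7.7, with the two wordings in the SAP and the silence of Protocol 9.4.2 leaving room for doubt. The plan should remove that doubt before the count is used.

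The overall size cannot be set from the documents and may be small. What can be said without assumption is that at each of the three looks one uncounted subject at the boundary changes the decision. The correction is worth making because it is cheap and uses data already collected.

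**What to change.** - **SAP 7.7:** state that related SAEs with onset after the 30-day window count as treatment-related for the stopping rule when they are known at a look. Keep the 30-day limit for all-causality TEAEs.
- **SAP 7.7.3:** include these events in the related-SAE summaries, flagged by timing, or add a separate table of related SAEs with onset more than 30 days after the last dose.
- **Wording:** align the two descriptions of the term in SAP 7.7 and 7.7.3, and change the affected table titles. Editing the sentence in 7.7 alone would leave late events excluded by title.
- **Protocol:** reconcile 8.3.1 with 8.3.3, and the two parts of Schedule of Activities footnote 17, on whether related-SAE reporting continues after alternative cancer treatment starts. The analysis definition should then follow the reconciled text.

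**Cost.** No new data are needed. Some titles and shells change, and related-SAE counts may rise slightly. Late events will be less completely ascertained than those within 30 days, which is the reason to flag them or show them apart.
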